The primary objective of this protocol is to investigate whether IV ghrelin, as compared to placebo, will increase motivation for alcohol reward, as measured by a progressive ratio (PR) schedule paradigm with IV alcohol self-infusion (primary aim). We will also assess a number of secondary aims. Specifically, we will also assess whether IV ghrelin, as compared to placebo, will also alter urges to drink and the subjective response to IV alcohol. Adverse events will also be assessed to ensure the safety of the IV co-administration of ghrelin and alcohol. During an “fMRI/alcohol clamp” session, fMRI will be used to see whether ghrelin affects the activation of the ventral striatum induced by acute IV alcohol administration and the incentive salience of cues associated with alcohol administration.

Study Population. Male and female participants will be non-treatment seeking heavy drinking volunteers.

Design. The study is designed as a within-subject, double-blind, placebo-controlled study of ghrelin. The first visit will be the initial screening visit. The second and third visits will be PR sessions with IV ethanol, during which each participant will also receive IV ghrelin (or matched placebo). The fourth and fifth visits will combine an fMRI session with an ‘alcohol clamp’ session (i.e. a fixed dose of alcohol will be administered) and subjects will participate in a modified version of the monetary incentive delay (MID) task in which they will respond to cues that indicate the opportunity to press a button to gain a reward. On some trials the reward will be points that can be exchanged for snack foods while on other trials the reward will be points that

will determine how much intravenous alcohol a subject will be given during the “alcohol clamp” procedure which will immediately follow the modified MID task. After the modified MID task is complete subjects will have a short break and then begin the alcohol IV infusion.

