- We will determine if ghrelin increases the incentive salience of alcohol predicting cues by using a modified version of the monetary incentive delay (MID) task. In this task subjects will button press to earn credits associated with subsequent alcohol administration, instead of monetary, reward. The MID task has been used extensively in neuroeconomic imaging research and the difference in BOLD signal in the ventral striatum (VS) between anticipation of responding for \$0 and anticipation of responding for \$5 is thought to measure the incentive salience of cues associated with monetary reward.^{140,141} We propose that the difference in striatal BOLD signal between anticipation of responding for a cue predicting no alcohol delivery and cues predicting delivery of alcohol will provide an objective measure of the incentive salience of cues associated with alcohol reward. Our hypothesis is that ghrelin increases the motivational value of alcohol cues. In addition to the VS, other fMRI regions-of-interest (ROI's) for this study are the amygdala, insula and orbitofrontal cortex (OFC), as IV ghrelin has already shown its ability to activate these areas,¹⁴² and all these areas play an important role in the neural systems model of alcoholism.^{20,101,109,112,143}
- In addition to using fMRI to examine ghrelin's effect on the incentive salience of alcohol cues, we will also use fMRI procedures we have developed¹⁴⁴ to examine the effect of ghrelin on the brain's response to IV alcohol. Our previous work has shown that IV

alcohol administration using the “alcohol clamp” procedure (NIAAA protocol 04-AA-0060) results in a robust increase in BOLD signal in the human ventral striatum. Thus, by administering alcohol during functional imaging we should be able to determine if ghrelin enhances the direct pharmacological effect of alcohol on the brain’s reward circuitry.

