The primary objective of this protocol is to investigate whether ghrelin alters alcohol's pharmacologic effects, including motivation for alcohol reward, as well as subjective measures of craving, and the subjective responses to alcohol in heavy drinkers receiving IV administrations of ghrelin and alcohol.

a. Primary objectives

The primary measure of this study will be the breakpoint, which is the schedule (number of button presses) at which the individual stops to work for more alcohol.

b. Secondary objectives

Secondarily, the BrAC exposure measures will also be determined, that is the highest (max) BrAC, average BrAC and the area under the BrAC-time curve determined for each subject. Urge to drink and alcohol sensitivity will be measured during the PR session. Adverse events will also be assessed in order to assess the safety of the IV co-administration of ghrelin and alcohol. Also, during the "fMRI/alcohol clamp" session, fMRI will be used to see whether ghrelin affects the activation of the ventral striatum (VS) in anticipation to work for alcohol reward and the incentive salience of cues in subjects who will subsequently receive IV alcohol administration. In

addition to the VS, other fMRI ROI's are the amygdala, insula and OFC. Adverse events will also be assessed during the fMRI/alcohol clamp sessions.

Furthermore, an additional secondary aim will be an exploratory analysis of the role of genetic polymorphisms of both ghrelin and ghrelin receptor genes – detailed in page 14 – as possible moderators of ghrelin's effects on the primary aim ('breakpoint', i.e. number of button presses in the IV alcohol PR procedure).

3. Subjects:

a. Description of study populations

Male and female adults will be eligible to participate in this study. Participants will be non-treatment seeking heavy drinking volunteers. Our goal is to screen 124 subjects and recruit 62 individuals. Assuming a 20% drop-out rate, we will reach 50 completers.

b. Inclusion criteria

1. Male and female participants between 21-60 years of age.
2. Good health as determined by medical history, physical exam, ECG and lab tests.
3. Creatinine \leq 2 mg/dl.

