After completion of the baseline modified MID task, subjects will receive the ghrelin/placebo bolus and followed by a continuous infusion as described above. During ghrelin/placebo infusion subjects will repeat the MID task and resting scans. Next, alcohol infusion begins, which will be given as described in protocol 08-AA-0137. Ethanol will be infused as a 6% v/v solution in saline. The infusion rates will be based on a physiologically-based pharmacokinetic model for ethanol – the same model used to compute the infusion rates for the alcohol self-administration sessions described above. Blood samples will be obtained during the clamp. The alcohol clamp method has been used successfully in several studies of the pharmacokinetics and pharmacological effects of ethanol in humans,¹⁵⁸⁻¹⁶⁵ and is has been used, for example, in NIAAA protocols listed above.

During the alcohol clamp, subjects will have resting scans and repeat the MID task. (See fMRI appendix flow sheet for details). At the end of the infusion, the catheters will be removed, lunch will be served and repeated BrACs will be performed until BrAC returns to 0.00 g%.

Diet (visits #2-5)

The night before each session, participants are admitted to the Clinical Center and will receive a standardized dinner. After overnight stay, participants will receive a fixed breakfast in the morning. These two courses will be standardized in agreement with the NIH CC Nutrition Service. Then, before starting the session, a fixed light snack is served (\approx 167 Kcal; approximately 62% carbohydrate, 13% protein, 25% fat) to standardize food intake before IV

ghrelin. The use of a standardized caloric food intake before the experiment: i) is a procedure used in human studies testing ghrelin i.v.^{35,37,75}; ii) is consistent with studies testing the role of ghrelin on alcohol reward in animals without food deprivation effect^{98,122}; iii) avoids the presence of elevated baseline ghrelin levels (present in food deprivation conditions^{34,74,81,91}), which may be a confounding factor for our controlled experiment (exogenous ghrelin vs. saline solution); iv) does not represent a confounding factor for the ethanol administration, as it is infused IV and not orally; and v) it is consistent with our similar procedure used in the IV ghrelin alcohol study at Brown University. Lunch will be provided after the end of each session. Water will be permitted *ad libitum*, while other beverages (e.g. soda) will not be permitted.

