Outcome data will be examined for homogeneity of variance, and if necessary transformed to meet this criterion. Most of the analyses will consist of repeated measures ANCOVAs to accommodate dependent measures assessed at multiple time points. When the dependent measure is just assessed once then a regular ANCOVA will be used. We will examine medication main effects across several different dependent measures.

Criteria for significance

A probability level of 0.05 or lower will be considered significant.

2. Power analysis

Power analysis

A generic calculation of power for a two-means comparison to detect an effect size of Cohen's $f \geq 0.4$ (large effect size) with a sample size of 50 yields a power estimate ≥ 0.80 at alpha=0.05. The relative effect size chosen (“large” effect size) for the power calculation is based on the observation that laboratory studies typically yield larger effect sizes than clinical trials, including, for example, our recent (unpublished; PI: [name]) human lab studies using the

IV Alcohol PR procedure, described above and representing the study our primary aim (number of button presses) is based upon.

Furthermore, the sample proposed here provides sufficient power (power estimate ≥ 0.80 at alpha=0.05) to detect ghrelin's effects on fMRI BOLD activation in the VS, consistent with the unpublished data (PI: [name]; data already mentioned above) with varenicline (n = 8) vs. placebo (n = 7) indicating significantly higher BOLD activation in the varenicline group.

Accrual number request, taking into account screening/ dropouts

In the Brown University study with IV ghrelin, inclusionary/exclusionary criteria were similar and about 50% of the subjects screened were eligible and randomized. Consistent with other human laboratory studies with a similar study length, we also expect that a number up to 20% will not complete the study. Therefore, we anticipate a number-needed-to-screen of 124 subjects, with 62 being randomized and 50 completers.

11. Human Subjects Protection

a. Subject selection

Adults who fulfill the qualification criteria will be included, regardless of race, ethnicity, sex, or religious affiliation.

b. Justification for inclusion of children

Children will not be included because the study proposed involves the administration of alcohol. It is illegal to give alcohol to individuals below 21 years of age.

c. Justification for inclusion or exclusion of other vulnerable subjects

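### The fMRI aim of showing that ghrelin enhances the brain's response to alcohol needs a medication-by-phase contrast, but the analysis section names only medication main effects, which cannot separate enhancement from a direct ghrelin effect

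*Combined protocol and SAP*

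**What the plan says.** The Precis states the imaging aim as learning "whether ghrelin affects the activation of the ventral striatum induced by acute IV alcohol administration". The Introduction (fMRI/alcohol clamp) repeats it: "by administering alcohol during functional imaging we should be able to determine if ghrelin enhances the direct pharmacological effect of alcohol".

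Section 4d (fMRI/alcohol clamp sessions) gives the order within a session. A baseline MID task comes first, then the ghrelin or placebo bolus and infusion. Before alcohol starts, "During ghrelin/placebo infusion subjects will repeat the MID task and resting scans". The alcohol clamp follows, with resting scans and the MID task again. Both imaging sessions give alcohol; only the drug differs.

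On direct effects, the Introduction adds amygdala, insula and OFC as regions of interest because "IV ghrelin has already shown its ability to activate these areas". The ventral striatum (VS) is listed apart from these three. For the VS, the Introduction offers a hypothesis that ghrelin raises the motivational value of alcohol cues, measured by striatal BOLD, and animal data on accumbal dopamine.

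Section 10 is the only analysis text. Most analyses will be "repeated measures ANCOVAs to accommodate dependent measures assessed at multiple time points", and "We will examine medication main effects across several different dependent measures". It names no interaction, phase contrast, reference scan or BOLD summary for the clamp.

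Section 2b words the VS objective differently: whether ghrelin "affects the activation of the ventral striatum (VS) in anticipation to work for alcohol reward".

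**The concern.** Asking whether ghrelin changes the activation that alcohol induces is asking whether the alcohol effect differs between drug conditions. A medication main effect answers another question: whether the signal differs between ghrelin and placebo. Where ghrelin shifts the signal by itself, the two answers can diverge, and the protocol's rationale expects such a shift in some or all of its regions.

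At stake is the mechanistic claim of a secondary aim. A significant main effect on clamp scans could be read as amplified alcohol reward when ghrelin acts alone. Section 2b adds to the looseness, because it replaces the alcohol-induced response with anticipation. With neither a contrast nor a consistently worded objective, the quantity of interest could be settled after the data are seen. The primary outcome, breakpoint, is not affected.

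**Working it through.** **The plan's own figure.** Section 10 claims power of at least 0.80 for a two-means comparison, Cohen's f of 0.4, N = 50, alpha 0.05 (taken as two-sided). For two equal groups d = 2f = 0.8. With 25 per group, power is 0.807 by the normal approximation and 0.791 by noncentral t. A paired test with n = 50 and standardised effect 0.4 gives 0.792. The figure reproduces, but for a two-means comparison, not for an interaction.

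**What each comparison contains.** Let g1 be ghrelin's direct effect before alcohol, g2 its direct effect during the clamp, and i the enhancement. The expected ghrelin-placebo differences are:

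- pre-drug scan: 0
- on-drug, pre-alcohol scan: g1
- clamp scan: g2 + i
- clamp minus pre-drug scan: g2 + i
- clamp minus on-drug pre-alcohol scan: g2 + i − g1, which equals i if g1 = g2

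Only the last removes a constant direct effect. Subtracting the pre-drug scan does not.

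**Assumptions.** n = 50 completers (Section 10). The SD of the ghrelin-placebo difference is 1 in each phase. The correlation r of that difference between phases is 0, 0.3 or 0.6. The documents supply neither SD nor r. Powers are noncentral t, two-sided 0.05.

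**No enhancement (i = 0), constant direct effect g.** The clamp-phase main effect has standardised effect g:

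- g = 0.2: significant in 28% of trials
- g = 0.3: 55%
- g = 0.4: 79%

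The phase contrast has expectation 0 and rejects in 5%.

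A separate simulation used scan SD 1, g = 0.4 and a common correlation of 0.3 to 0.7 among scans. It gave 66% to 95% for clamp scans, 40% to 71% for change from the pre-drug scan, and about 5% for the phase contrast.

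**Power cost.** With i = 0.4 and no direct effect, the main effect has power 0.79. The phase contrast has SD √(2(1−r)) and standardised effect 0.4/√(2(1−r)):

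- r = 0: 0.4/1.414 = 0.283, power 0.50
- r = 0.3: 0.4/1.183 = 0.338, power 0.65
- r = 0.6: 0.4/0.894 = 0.447, power 0.87

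**Fading direct effect.** Section 4d gives a bolus of 3 mcg/kg over 10 minutes (3000/10 = 300 ng/kg/min), then 16.9 ng/kg/min for 65 minutes. The clamp lasts 35 minutes. If infusion and clamp end together (an assumption), about 65 − 35 = 30 minutes of infusion precede alcohol. The Introduction quotes post-bolus half-lives of 10 to 47 minutes, so g2 may be smaller than g1. With g1 = 0.4, g2 = 0.2 and i = 0, the contrast has expectation −0.2:

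- r = 0: 0.2/1.414 = 0.141, rejects in about 16% (simulated 15.9%, noncentral t 16.5%)
- r = 0.3: 0.2/1.183 = 0.169, about 22%
- r = 0.6: 0.2/0.894 = 0.224, about 34%

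These rejections point towards reduced enhancement.

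**The case against.** A reader might infer that a direct ghrelin effect would be reported as an enhanced alcohol effect. The documents do not go that far. A repeated measures model can carry a phase term, and a medication effect on an outcome defined as alcohol-induced change from the on-drug scan would itself be the right contrast. Section 10 neither rules these out nor says they will be used. What stands is that the stated analysis cannot distinguish the two explanations.

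A reader might also infer that IV ghrelin is known to activate the VS. The protocol says this only of amygdala, insula and OFC. For the VS it has a hypothesis about cue response and animal dopamine data, so the size and existence of a direct VS effect are open.

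The MID measure is a within-scan difference between cues, so a uniform ghrelin shift cancels there. A cue-specific ghrelin effect, which the protocol hypothesises, does not cancel. Resting scans have no such internal reference.

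Scan timing and detail are referred to an appendix flow sheet and to related protocols that are not in the text reviewed. They may define the scans more fully, but Section 10 makes no reference to them for the analysis.

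The mismatch in Section 2b should not be pressed too far. Section 2 opens by asking whether ghrelin alters alcohol's pharmacologic effects, and Section 9b lists BOLD in reward circuitry during the clamp session as an outcome. What is missing is a VS objective worded as response to alcohol.

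Finally, the phase contrast is no clean remedy. Its 5% error rate requires a constant direct effect, and its power can fall well below that of the main effect. Both objections stand and belong in the plan.

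**Conclusion.** The concern holds as a gap in the analysis plan, not in the scans collected. The aim calls for a medication-by-phase contrast and the plan names only medication main effects. With no enhancement and a constant direct effect of 0.2 to 0.4, the main effect on clamp scans is significant in 28% to 79% of trials, and change from the pre-drug scan does not cure this.

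These percentages are illustrative: they rest on assumed effect sizes, 50 pairs and a unit SD. The conclusion that the main effect confounds the two does not depend on them; how much it matters in the VS does. This should be corrected before analysis, but it concerns a secondary aim.

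**What to change.** In Section 10, pre-specify for the VS and each other region of interest, separately for resting and MID scans: (clamp scan minus on-drug pre-alcohol scan) under ghrelin, minus the same under placebo. Report the pre-alcohol ghrelin-placebo difference separately as ghrelin's direct effect. Reword Section 2b so that it carries the alcohol-response objective of the Precis and Introduction alongside anticipation.

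No new scan, visit or participant is needed. State two downsides with the contrast:

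- **Power.** Give the range shown above (about 0.50 to 0.87 for a true effect of 0.4, against about 0.79 for the main effect). Replace the assumed SD and correlation with values from the group's existing scans, if available. The main effect's power is for a different question.
- **Timing.** There is no alcohol-free session, so phase is tied to time since the bolus. Under the halving scenario above, the contrast rejects in about 16% to 34% of trials, towards reduced enhancement. Record this as a limitation on interpreting a negative or null contrast.
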